
 To evaluate the efficacy of itepekimab compared to placebo. To evaluate the safety and tolerability of itepekimab compared to placebo in participants with CRSwNP. To evaluate the PK of itepekimab. Assessment of immunogenicity to itepekimab over time compared to placebo. 	
 Time to first either SCS or surgery for CRS in participants with AERD. Change from baseline to Weeks 24 and 52 in pre-BD FEV1 (in mL) in participants with AERD. Proportion of NPS responders at Weeks 24 and 52 (defined as participants with improvement by at least 1 point in NPS). Proportion of NPS responders at Weeks 24 and 52 (defined as participants with improvement by at least 2 points in NPS). Incidence of TEAEs, TESAEs, TEAESIs and TEAEs leading to treatment discontinuation. Itepekimab concentration in serum. Incidence of treatment-emergent anti-itepekimab antibody (ADA) responses throughout the study.

Abbreviations: ACQ = asthma control questionnaire; ADA = anti-drug antibody; AERD = aspirin-exacerbated respiratory disease; BD = bronchodilator; CRS = chronic rhinosinusitis; CRSwNP = chronic rhinosinusitis with nasal polyposis; CT = computed tomography; FEV = forced expiratory volume; LMK = Lund Mackay Score; NCS = Nasal Congestion Score; NP = nasal polyp; NPS = Nasal Polyposis Score; PK = pharmacokinetic(s); PROMIS = Patient-Reported Outcomes Measurement Information System; SCS = systemic corticosteroids; SD-SF = sleep disturbance short form; SNOT = Sino-Nasal Outcome Test; TEAE = treatment-emergent adverse event; TESAЕ = treatment-emergent serious adverse event; TEAESI = treatment-emergent adverse events of special interest; TSS = total symptoms score; UPSIT = University of Pennsylvania Smell Identification Test.

a Initiation of rescue therapy as defined in [Section 6.9.1](#). A course of SCS is considered continuous if intervention is separated by less than 7 days.

For China, please see [Section 10.8.1](#) details.

Overall design synopsis:

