 - b) Study intervention discontinuation.
 - c) Use of other prohibited/rescue medications prior to Week 24.

Missing data handling:

After applying the rules for IEs, if there is still missing data, then the missing data will be handled as follows:

- For participants who discontinue IMP before Week 24 without use of selected prohibited/rescue medication (eg, prohibited biologic therapy) or nasal/sinus surgery prior to Week 24: MI approach will be used to impute missing endpoint value at Week 24, and this MI will use all participants from the same randomized arm, excluding participants who use selected prohibited/rescue medication (eg, prohibited biologic therapy) or nasal/sinus surgery prior to Week 24.

Each of the imputed complete datasets will be analyzed by fitting an ANCOVA model with the baseline covariate and factors for treatment, asthma/AERD and region. Statistical inference obtained from all imputed data will be combined using Rubin's rule. Descriptive statistics including number of participants, mean, standard error, and LS means will be provided. In addition, difference in LS means and the corresponding 95% CI will be provided along with the p-values.

- **Main secondary endpoints:**

- a) **Continuous efficacy endpoints** including change from baseline in NPS and in NCS at Week 52, change from baseline in LMK score at Week 24, change from baseline in TSS, in Loss of Smell Symptom Severity score, in UPSIT score, in SNOT-22 total score and in PROMIS SD-SF-8b at Week 24 and Week 52: these endpoints will be analyzed in the same fashion as the co-primary endpoints described in [Section 9.2.2.2](#).
- b) **Proportion endpoints**, including proportion of participants with CRSwNP requiring SCS or surgery for CRS during the planned study intervention period and proportions of NPS responders, will be analyzed using an MH method stratified by asthma/AERD strata and region. The estimate of the MH weighted risk difference and corresponding Wald 95% CI and Wald test using Sato variance will be provided. All data collected after study intervention discontinuation will be used in the analysis. Participants who discontinue the study without an event will be considered as no event.

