
 To evaluate the efficacy of itepekimab compared to placebo. To evaluate the safety and tolerability of itepekimab compared to placebo in participants with CRSwNP. To evaluate the PK of itepekimab. Assessment of immunogenicity to itepekimab over time compared to placebo. 	
 Annualized rate of SCS course or surgery for CRS during the planned study intervention period in participants with AERD. Time to first either SCS or surgery for CRS in participants with AERD. Change from baseline to Weeks 24 and 52 in pre-BD FEV1 (in mL) in participants with AERD. Proportion of NPS responders at Weeks 24 and 52 (defined as participants with improvement by at least 1 point in NPS). Proportion of NPS responders at Weeks 24 and 52 (defined as participants with improvement by at least 2 points in NPS). Incidence of TEAEs, TESAEs, TEAESIs and TEAEs leading to treatment discontinuation. Itepekimab concentration in serum. Incidence of treatment-emergent anti-itepekimab antibody (ADA) responses throughout the study.
Tertiary/Exploratory	

 To evaluate the effect of itepekimab on overall health status, cough, PGIS and PGIC. To evaluate the efficacy of itepekimab compared to placebo in CRSwNP quality of life. To evaluate the effects of itepekimab compared to placebo on total sinus opacification. To evaluate the effect of itepekimab on health care resource use/productivity compared to placebo. To evaluate the early effect of itepekimab compared to placebo on lung function and asthma in the subgroup of participants with co-morbid asthma. 	
 Change from baseline to Weeks 24 and 52 in the EQ-5D index and VAS. Change from baseline to Weeks 24 and 52 in PGIS score for each symptom and for symptoms overall. PGIC score at Weeks 24 and 52 for each symptom and for symptoms overall. Change from baseline to Weeks 24 and 52 in Leicester Cough Questionnaire total score. Proportion of SNOT-22 responders at Weeks 24 and 52 (defined as participants with improvement of at least 8.9 points in SNOT-22). Change from baseline to Week 24 in sinus (all sinuses) percent opacification volume assessed by CT scan. Cumulative number of health care resource utilization by visit type. Change from baseline to Weeks 24 and 52 in WPAI-SHP on overall work impairment and daily activity impairment. Change from baseline to Weeks 4 in pre-BD FEV1.

Objectives	Endpoints

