6.3 ASSIGNMENT TO STUDY INTERVENTION

All participants will be centrally assigned to randomized study intervention using an IRT. Before the study is initiated, the telephone number and call-in direction for the Interactive Voice Response System (IVRS) and/or the log in information and direction for the Interactive Web Response System (IWRS) will be provided to each site.

Definition of a randomized participant is a participant from screened population who has been allocated to a randomized intervention regardless of whether the intervention was received or not. A participant cannot be randomized more than once in the study. The randomized intervention kit number list is generated centrally by Sanofi. The IMPs are packaged in accordance with this list. Study intervention will be dispensed at the study visits as summarized in the SoA ([Section 1.3](#)).

During the randomization process, participants will be stratified by asthma/AERD status (no asthma, asthma only, asthma & AERD), and region (Asia or rest of the world).

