9.2.2.2 Main analytical approach

The 2 co-primary endpoints will be analyzed with the primary estimand defined according to the following attributes:

- Endpoint: change from baseline to Week 24 in NPS and NCS.
- Intervention condition: itepekimab 300 mg Q2W and itepekimab 300 mg Q4W will be compared to placebo, on top of background therapy.
- Analysis population: intent-to-treat (ITT) population.
- Intercurrent events:
 - The following IEs will be handled with a composite variable strategy. Data after the IE will be assigned to the worst possible score:
 - a) Use of selected prohibited/rescue medication (eg, prohibited biologic therapy) prior to Week 24.
 - b) Nasal/sinus surgery prior to Week 24.

- The following IEs will be handled with a treatment policy strategy. All assessments after starting such IE and before or at Week 24 will be included:
 - a) Use of SCS for any reason.
 - b) Study intervention discontinuation.
 - c) Use of other prohibited/rescue medications prior to Week 24.
- Population-level summary: difference in LS means between itepekimab and placebo from ANCOVA model with change from baseline to Week 24 in NPS and NCS as response variables, intervention group (itepekimab 300 mg SC Q2W, itepekimab 300 mg Q4W, or placebo) and randomization stratification factors (asthma/AERD status and regions) as fixed effects, and the baseline value as covariates. The corresponding 95% CI will be provided along with the p-value. In addition, descriptive statistics including number of participants, mean, SEM, and LS means will be provided for each intervention group.
- Missing data handling.

After applying the rules for IEs, if there is still missing data, then the missing data will be handled as follows:

- For participants who discontinue IMP before Week 24 without use of selected prohibited/rescue medication (eg, prohibited biologic therapy) or nasal/sinus surgery prior to Week 24: MI approach will be used to impute missing endpoint value at Week 24, and this MI will use all participants from the same randomized arm, excluding participants who use selected prohibited/rescue medication (eg, prohibited biologic therapy) or nasal/sinus surgery prior to Week 24.

Each of the imputed complete data will be analyzed by fitting the ANCOVA model. Statistical inference obtained from all imputed data will be combined using Rubin's rule.

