9.2.3 Secondary endpoint(s) analyses

The secondary endpoints detailed in this section are as follows:

- **Continuous efficacy endpoints** including change from baseline in NPS and in NCS at Week 52, change from baseline in LMK score at Week 24, change from baseline in TSS, in Loss of Smell Symptom Severity score, in UPSIT score, in SNOT-22 total score and PROMIS SD-SF-8b score at Week 24 and Week 52: these endpoints will be analyzed in the same fashion as the co-primary endpoints described in [Section 9.2.2.2](#).
- **Proportion endpoints**, including proportion of participants with CRSwNP requiring SCS or surgery for CRS during the planned study intervention period and proportions of NPS responders, will be analyzed using an MH method stratified by asthma/AERD strata and region. The estimate of the MH weighted risk difference and corresponding Wald 95% confidence interval and Wald test using Sato variance will be provided. All data collected after study intervention discontinuation will be used in the analysis. Participants who discontinue the study without an event will be considered as no event.
- **Time to first SCS use or surgery for CRS** will be analyzed using a Cox regression model. The time to the first event will be included as the dependent variable while intervention group, asthma/AERD strata and region will be used as covariates. The HR will be estimated for comparison of each Itepekimab regimen to placebo. The Kaplan-Meier method will be used to derive the probabilities that a participant would experience an event up to specific time points for each intervention group.
- **The annualized number of SCS course or surgery for CRS** during the planned study treatment will be analyzed using a negative binomial regression model. The model will include the number of SCS course or surgery for CRS during the planned study treatment period as the response variable, with intervention group, asthma/AERD strata and regions. Log transformed treatment duration will be the offset variable. The estimated annualized number of SCS courses or surgery for CRS for each treatment group and its 95% CI will be derived from the negative binomial model. The event rate ratio of each Itepekimab regimen versus placebo and the corresponding 95% CI and p-values will be provided.

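### The NPS responder analysis leaves out baseline NPS: the Mantel-Haenszel estimate is valid, but adding the covariate is a cheap way to recover whatever precision baseline carries

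*Protocol*

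**What the plan says.** Section 3 (Table 2) lists two NPS responder endpoints, each at Weeks 24 and 52: "defined as participants with improvement by at least 1 point in NPS" and "defined as participants with improvement by at least 2 points in NPS". The synopsis lists the same endpoints.

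For proportion endpoints, Section 9.2.3 states the method as "will be analyzed using an MH method stratified by asthma/AERD strata and region", and adds: "The estimate of the MH weighted risk difference and corresponding Wald 95% confidence interval and Wald test using Sato variance will be provided". The synopsis (1.1, item b) agrees: "proportions of NPS responders, will be analyzed using an MH method stratified by asthma/AERD strata and region". The strata are those of the randomization (Section 6.3): "participants will be stratified by asthma/AERD status (no asthma, asthma only, asthma & AERD), and region (Asia or rest of the world". Baseline NPS is not among them.

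For the change in NPS, Section 9.2.2.2 fits an ANCOVA with "randomization stratification factors (asthma/AERD status and regions) as fixed effects, and the baseline value as covariates". Section 9.2.3 carries that model over to Week 52. Under Section 8.2.2, the baseline for the NPS analysis is the central reading of the Visit 2 endoscopy, so the value is already collected.

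**The concern.** A responder is someone whose score has fallen by a set amount from the Visit 2 reading, so the baseline value is part of the outcome. If participants with higher readings tend to fall further, through true severity or through reading error that regresses to the mean, baseline NPS predicts response. Neither the randomization nor the MH analysis uses it.

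The protocol fixes this method itself rather than leaving it to the SAP, and it adjusts for baseline when the same score is analyzed as a continuous change. What is at stake is the width of the intervals for the responder differences. Section 9.2.5 places a selected set of secondary endpoints under type I error control and leaves the list to the SAP. If the responders are on it, the gain would bear on a formal test.

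**Working it through.** **1. The protocol's own figures.** Inputs from Sections 9.2.5 and 9.4: 70 per arm, two-sided alpha 0.049, NPS difference -1.10 with SD 1.79, NCS difference -0.55 with SD 0.9.

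- NPS: SE = 1.79 x sqrt(2/70) = 0.303. Power is 95.2% (normal) or 95.0% (t). Minimal detectable difference is 0.601.
- NCS: SE = 0.9 x sqrt(2/70) = 0.152. Power is 95.0% (normal) or 94.8% (t). Minimal detectable difference is 0.302.
- Combined: 0.95 x 0.95 = 90.25%, or 90.0% from the t-test values.

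The stated 95%, 95%, at least 90%, -0.60 and -0.30 are reproduced. They rest on an unadjusted t-test, and the protocol states no power for the responder endpoints. Nothing in Section 9.4 depends on this point.

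**2. Simulation set-up.** 4000 trials per setting, one active arm against placebo.

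- From the protocol: 70 per arm, SD of change 1.79, difference -1.10, six strata (3 x 2), response as a fall of at least 1 or at least 2 points, alpha 0.049.
- Assumed: baseline NPS 5/6/7/8 with probabilities 0.35/0.35/0.15/0.15 (mean 6.10, SD 1.04); asthma/AERD shares 35/40/25%; 30% Asia; strata not prognostic; placebo mean change -0.1; slope of change on baseline from 0 to -0.8, so r = slope x 1.04/1.79 runs from 0 to -0.47. Scores were rounded and bounded to 0-8.

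In each stratum, let a of n1 active and c of n0 placebo participants respond, with N = n1 + n0. The MH estimate is RD = sum[(a n0 - c n1)/N] / sum[n1 n0/N], with the Sato variance. The comparison was a linear model for response with treatment, strata main effects and baseline NPS, using a robust SE.

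**3. Results.** The variance ratio is adjusted over MH.

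| r (assumed) | Variance ratio, >=1 / >=2 points | Power, >=1 point, MH to adjusted | Power, >=2 points, MH to adjusted |
|---|---|---|---|
| 0 | 0.996 / 0.997 | 82% to 82% | 78% to 77% |
| -0.12 | 0.98 / 0.98 | 82% to 82% | 78% to 78% |
| -0.23 | 0.96 / 0.94 | 82% to 83% | 78% to 79% |
| -0.35 | 0.92 / 0.92 | 81% to 83% | 79% to 81% |
| -0.47 | 0.86 / 0.85 | 81% to 87% | 78% to 83% |

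A hand check: the ratio should be near 1 minus the squared correlation of baseline with response. At r = -0.47 that correlation was 0.360 (>=1) and 0.371 (>=2), giving 1 - 0.130 = 0.87 and 1 - 0.138 = 0.86.

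A separate run used the logistic standardized estimator itself (3000 trials per setting, baseline SD 1.03, placebo change -0.3). It gave 0.994/1.002 at r = 0, 0.969/0.980 at -0.2, 0.949/0.948 at -0.3 and 0.892/0.893 at -0.4.

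Simulated active-arm response was about 65% and 43%, near the reference rates of about 65% and 46% in Section 2.1.

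**4. Validity of MH.** MH averaged 0.238-0.242 (>=1) and 0.213-0.217 (>=2), and the adjusted estimate agreed within 0.001. With no treatment effect, at r = -0.23 and -0.47, MH rejected in 5.7% and 5.7% (>=1) and in 6.2% and 6.1% (>=2). The adjusted test rejected in 5.7% and 5.2%, and in 6.1% and 5.6%. Both are slightly above 4.9%, which is mainly small-sample Wald behavior.

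**5. Chance imbalance.** The SD of the between-arm difference in mean baseline is 1.04 x sqrt(2/70) = 0.18. For >=1 point, response probability rises by 0.085 per NPS point at r = -0.23 and by 0.172 at r = -0.47. A one-SD imbalance therefore moves the risk difference by 0.18 x 0.085 = 1.5 or 0.18 x 0.172 = 3 percentage points, against an SE of about 8.

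**6. Is a negative r plausible?** Fix the SD of change at 1.79 and assume a baseline SD of 1.03. A baseline-to-Week-24 correlation of about 0.5 is then needed for r = 0. Correlations of 0.4, 0.3 and 0.2 give r = -0.14, -0.27 and -0.39. The protocol states neither correlation.

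**The case against.** The case for leaving the text alone is substantial. The synopsis and Section 9.2.3 agree, and the MH strata are exactly the randomization strata. MH gives a marginal risk difference without an outcome model. The change in NPS at Weeks 24 and 52 is already baseline-adjusted, the responder endpoints are neither primary nor key secondary, and no power claim rests on them. The gain is nil at r = 0, about one point of power at r = -0.23, and 5-6 points only at r = -0.47. All of this stands, and it sets the severity.

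Stronger readings are tempting but not supported:

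- A reader might infer that MH is biased, or that chance imbalance in baseline NPS is a defect the analysis fails to correct. Under randomization such imbalance is random variation, and the Sato standard error already covers it.
- A reader might take the loss of precision as established. The protocol gives no baseline-change correlation, so the loss is conditional.
- A reader might see a contradiction with the ANCOVA. Nothing in the protocol requires every analysis to carry that model's covariates.
- A reader might expect continuous and responder results to diverge because only one is adjusted. The two risk-difference estimates agree on average, and dichotomizing is itself an obvious reason for results to differ.

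The entry range of 5 to 8 does narrow baseline spread, but not strictly. Eligibility rests on the Visit 1 central and Visit 2 local readings, and the Visit 2 central reading used as baseline is made later, so it can fall below 5.

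The SAP could add a baseline-adjusted analysis. The point concerns the method that the protocol itself names.

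**Conclusion.** A low-severity efficiency point, not an error. The protocol's responder analysis is valid and unbiased and every stated figure stands, but it omits a covariate that is already collected, enters the outcome definition and is used in the ANCOVA of the same score. The cost is zero if baseline NPS does not predict change, about 2-8% of the variance for r of about -0.12 to -0.35, and about 15% at r = -0.47, with 0 to about 6 points of power. These sizes rest on the assumed r, baseline distribution and placebo change. The sample size, SD and treatment difference are the protocol's.

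**What to change.** In 1.1 item b and in 9.2.3, before unblinding and for the NPS responder endpoints only (>=1 and >=2 points, Weeks 24 and 52), prespecify a logistic regression with intervention group, asthma/AERD stratum, region and baseline NPS. Report the standardized (g-computation) risk difference with a robust or delta-method 95% CI and p-value. Keep the stratified MH estimate as sensitivity analysis and as fallback if the model does not converge. Leave MH in place for the SCS/surgery proportion.

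The cost is one wording change and a few lines of code. The downside is slight model dependence, which the MH sensitivity analysis would show. At r = 0 the change costs essentially nothing (variance ratio 0.994 to 1.002).

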1.2 SCHEMA

Figure 1 - Graphical study design

Abbreviations: D = day; EOS = end of study; EOT = end of treatment; IMP = investigational medicinal product; MFNS = mometasone furoate nasal spray; N = number; Q2W = once every 2 weeks; Q4W = once every 4 weeks; R = randomization; SC = subcutaneous; V = visit; W = week.

a Itepekimab 300 mg administered as 1 SC injection Q2W. Q4W dosing will receive alternating doses of the active IMP and placebo Q2W.

b Placebo, administered as 1 SC injection of matching placebo to itepekimab SC Q2W.

c For participants not entering the long-term extension study.

d MFNS administered as 2 actuations per nostril twice a day (total daily dose of 400 µg), starting at Visit 1, unless they are unable to tolerate or there is a specific regulatory requirement preventing use of this dose in which case they can stay on a lower dose regimen (200 µg) of MFNS. In Japan, participants on INCS (MFNS or other INCS) will continue taking their daily INCS with a stable dose through all periods of the study. In Japan, participants not on INCS prior to screening, will receive MFNS during screening and throughout the study. China participants should be on daily treatment with intranasal corticosteroids (INCS) which may include MFNS, prior to screening and will continue their daily INCS with a stable dose as background treatment during the screening and throughout the study.

1.3 SCHEDULE OF ACTIVITIES (SOA)

Procedure	Screening ^a	Intervention Period										EOT/ETD ^b	Follow-up (20 weeks) /EOS ^c	Notes
		0	2	4	6, 8, 10	12	14, 16, 18, 20, 22	24	26, 28, 30, 32, 34	36	38, 40, 42, 44, 46, 48, 50			
Week	-4	0	2	4	6, 8, 10	12	14, 16, 18, 20, 22	24	26, 28, 30, 32, 34	36	38, 40, 42, 44, 46, 48, 50	52	72	
Visit ^d	1 (site)	2 (site)	3 (site)	4 (site)	5-7 (home/call)	8 (site)	9-13 (home/call)	14 (site)	15-19 (home/call)	20 (site)	21-27 (home/call)	28 (site)	29 (site)	
Days ^e	-28	1	15	29	43, 57, 71	85	99, 113, 127, 141, 155	169	183, 197, 211, 225, 239	253	267, 281, 295, 309, 323, 337, 351	365	505	
Informed consent ^f	X													
Inclusion and exclusion criteria	X	X												[Recheck clinical status before randomization and/or first dose of investigational intervention.]
Participant demographics	X													
Medical/surgical history ^g	X													Substances: [drugs, alcohol, tobacco, and caffeine]
AERD screening questionnaire ^h	X													
Record planned endoscopic sinus surgery ⁱ	X	←-----> Every 2 weeks												
Nasal endoscopy ^j	X	X						X				X	X	Central reading

Procedure	Screening ^a	Intervention Period										EOT/ETD ^b	Follow-up (20 weeks) /EOS ^c	Notes
		0	2	4	6, 8, 10	12	14, 16, 18, 20, 22	24	26, 28, 30, 32, 34	36	38, 40, 42, 44, 46, 48, 50			
Week	-4	0	2	4	6, 8, 10	12	14, 16, 18, 20, 22	24	26, 28, 30, 32, 34	36	38, 40, 42, 44, 46, 48, 50	52	72	
Visit ^d	1 (site)	2 (site)	3 (site)	4 (site)	5-7 (home/call)	8 (site)	9-13 (home/call)	14 (site)	15-19 (home/call)	20 (site)	21-27 (home/call)	28 (site)	29 (site)	
Days ^e	-28	1	15	29	43, 57, 71	85	99, 113, 127, 141, 155	169	183, 197, 211, 225, 239	253	267, 281, 295, 309, 323, 337, 351	365	505	
Prior/concomitant/rescue medications	X	-----> Every 2 weeks										X		
Smoking status	X	X	X	X		X		X		X		X	X	Smoking history at Visit 1 and smoking status at all other indicated visits
Study intervention administration														
IRT	X	X	X	X		X		X		X		X		
Randomization		X												
IMP administration ^k		-----> Q2W												
AxMP dispensation		----->												
Efficacy assessments														
CT scan ^l		X						X						
Dispense/collect symptom diary ^m	X												X	

Procedure	Screening ^a	Intervention Period										EOT/ETD ^b	Follow-up (20 weeks) /EOS ^c	Notes
		Week	-4	0	2	4	6, 8, 10	12	14, 16, 18, 20, 22	24	26, 28, 30, 32, 34			
Visit ^d	1 (site)	2 (site)	3 (site)	4 (site)	5-7 (home/call)	8 (site)	9-13 (home/call)	14 (site)	15-19 (home/call)	20 (site)	21-27 (home/call)	28 (site)	29 (site)	
Days ^e	-28	1	15	29	43, 57, 71	85	99, 113, 127, 141, 155	169	183, 197, 211, 225, 239	253	267, 281, 295, 309, 323, 337, 351	365	505	
Spirometry in participants with asthma only ⁿ		X		X				X				X	X	
SNOT-22 ^o		X		X		X		X		X		X	X	
Symptom Diary ^m	←----- Daily -----→													
UPSIT (in countries where available)		X						X				X		
ACQ-5 in participants with asthma only ^o		X		X		X		X				X	X	
EQ-5D-5L ^o		X				X		X		X		X	X	
PROMIS SD-SF-8b ^o		X				X		X		X		X		
Leicester cough questionnaire ^o		X				X		X				X		
HCRU		X				X		X		X		X	X	
WPAI-SHP ^o	←----- Q4W -----→													
PGIS ^o		X				X		X		X		X	X	
PGIC ^o						X		X		X		X	X	

Procedure	Screening ^a	Intervention Period										EOT/ETD ^b	Follow-up (20 weeks) /EOS ^c	Notes
		0	2	4	6, 8, 10	12	14, 16, 18, 20, 22	24	26, 28, 30, 32, 34	36	38, 40, 42, 44, 46, 48, 50			
Week	-4	0	2	4	6, 8, 10	12	14, 16, 18, 20, 22	24	26, 28, 30, 32, 34	36	38, 40, 42, 44, 46, 48, 50	52	72	
Visit ^d	1 (site)	2 (site)	3 (site)	4 (site)	5-7 (home/call)	8 (site)	9-13 (home/call)	14 (site)	15-19 (home/call)	20 (site)	21-27 (home/call)	28 (site)	29 (site)	
Days ^e	-28	1	15	29	43, 57, 71	85	99, 113, 127, 141, 155	169	183, 197, 211, 225, 239	253	267, 281, 295, 309, 323, 337, 351	365	505	
Safety assessments														
Physical examination Full = Mandatory Brief = if clinically indicated	Full	Brief	Brief	Brief		Brief		Brief		Brief		Full	Brief	
Vital signs ^o	X	X	X	X		X		X		X		X		
12-Lead ECG ^q	X											X		
Hematology, clinical chemistry ^r	X					X		X		X		X	X	
Urine analysis ^s	X							X				X		Central urinalysis
TB testing	X													Per local guidelines (local laboratory)
Hepatitis and HIV serology tests ^t	X													
Pregnancy (β-HCG blood) test ^u	X													

Procedure	Screening ^a	Intervention Period										EOT/ETD ^b	Follow-up (20 weeks) /EOS ^c	Notes
		0	2	4	6, 8, 10	12	14, 16, 18, 20, 22	24	26, 28, 30, 32, 34	36	38, 40, 42, 44, 46, 48, 50			
Week	-4	0	2	4	6, 8, 10	12	14, 16, 18, 20, 22	24	26, 28, 30, 32, 34	36	38, 40, 42, 44, 46, 48, 50	52	72	
Visit ^d	1 (site)	2 (site)	3 (site)	4 (site)	5-7 (home/call)	8 (site)	9-13 (home/call)	14 (site)	15-19 (home/call)	20 (site)	21-27 (home/call)	28 (site)	29 (site)	
Days ^e	-28	1	15	29	43, 57, 71	85	99, 113, 127, 141, 155	169	183, 197, 211, 225, 239	253	267, 281, 295, 309, 323, 337, 351	365	505	
Urine pregnancy test ^u		<----->											X	
AEs/SAEs		<----->												
PK and ADA														
Serum PK samples for itepekimab concentration ^v		X		X		X		X		X		X	X	
Anti-itepekimab antibody ^v		X				X		X				X	X	
Biomarkers														
Blood biomarkers ^w		X		X		X		X				X	X	
Nasal Absorption biomarkers (optional) ^x		X		X		X		X				X		
Urine biomarkers ^y		X		X		X		X				X		
Nasal brushing for RNA and cytology (optional) ^z		X		X				X				X		
Archival Serum/Plasma (optional) ^{aa}		X		X		X		X				X		

Procedure	Screening ^a	Intervention Period										EOT/ETD ^b	Follow-up (20 weeks) /EOS ^c	Notes
		0	2	4	6, 8, 10	12	14, 16, 18, 20, 22	24	26, 28, 30, 32, 34	36	38, 40, 42, 44, 46, 48, 50			
Week	-4	0	2	4	6, 8, 10	12	14, 16, 18, 20, 22	24	26, 28, 30, 32, 34	36	38, 40, 42, 44, 46, 48, 50	52	72	
Visit ^d	1 (site)	2 (site)	3 (site)	4 (site)	5-7 (home/call)	8 (site)	9-13 (home/call)	14 (site)	15-19 (home/call)	20 (site)	21-27 (home/call)	28 (site)	29 (site)	
Days ^e	-28	1	15	29	43, 57, 71	85	99, 113, 127, 141, 155	169	183, 197, 211, 225, 239	253	267, 281, 295, 309, 323, 337, 351	365	505	
Whole blood DNA/ IL-33/ST2 genomic variant analyses (optional) ^{aa}		X												

Abbreviations: ACQ = asthma control questionnaire; ADA = antidrug antibody; AE = adverse event; AERD = aspirin-exacerbated respiratory disease; AESI = adverse event of special interest; ALT = alanine aminotransferase; AST = aspartate aminotransferase; ATS = American Thoracic Society; AxMP = auxiliary medicinal product; BD = bronchodilator(s); CT = computed tomography; CRSwNP = chronic rhinosinusitis with nasal polyposis; DNA = deoxyribonucleic acid; ECG = electrocardiography; eDiary = electronic diary; eCRF = electronic case report form; ECP = eosinophil cationic protein; CRP = C-reactive protein; CSF = colony stimulating factor; CXCL = chemokine (C-X-C motif) ligand; EOS = end of study; EQ-5D-5L = EuroQol-5 dimension-5 level; EOT = end of treatment; ERS = European Respiratory Society; ETD = early treatment discontinuation; FEF = forced expiratory flow; FEV = forced expiratory volume; FVC = forced vital capacity; GGT = gamma-glutamyl transferase; HBcAb = hepatitis B core antibody; HBsAb = hepatitis B surface antibody; HBsAg = hepatitis B surface antigen; HBV = hepatitis B virus; HCG = human chorionic gonadotropin; HCRU = health care resource utilization; HCV = hepatitis C virus; HCVAb = hepatitis C virus antibodies; HIV = human immunodeficiency virus; IEC = Independent Ethics Committee; IFN-γ = interferon-gamma; Ig = immunoglobulin; IL = interleukin; IMP = investigational medicinal product; INCS = intranasal corticosteroids; IRB = Institutional Review Board; IRT = interactive response technology; ISR = injection site reaction; LABA = long-acting beta-agonists; LAMA = long-acting muscarinic antagonist; LTE4 = Leukotriene E4; LTS = long-term study; MFNS = mometasone furoate nasal spray; NCS = Nasal Congestion Score; NPS = Nasal Polyposis Score; PGIC = Patient Global Impression of Change; PGIS = Patient Global Impression of Severity; PGx = pharmacogenomics; PK = pharmacokinetics; PRO = patient-reported outcome; PROMIS = Patient-Reported Outcomes Measurement Information System; Q2W = every 2 weeks; Q4W = every 4 weeks; RNA = ribonucleic acid; SAE = serious adverse event; SCS = systemic corticosteroids; SD-SF = Sleep Disturbance Short Form; SNOT = Sino-Nasal Outcome Test; SoA = schedule of activities; TARC = thymus and activation-regulated chemokine; TB = tuberculosis; TNF = tumor necrosis factor; TSS = Total Symptom Score; UPSIT = University of Pennsylvania Smell Identification Test; sST2 = soluble suppression of tumorigenicity 2; WOCBP = women of childbearing potential; WPAI-SHP = Work Productivity and Activity Impairment Specific Health Problem.

- a The screening period is 28 days +/- 7 days in duration to run in any participant on MFNS, and to collect baseline data. In Japan, participants on INCS (MFNS or other INCS) will continue taking their daily INCS with a stable dose through all periods of the study. In Japan, participants not on INCS prior to screening, will receive MFNS during screening and throughout the study. China participants should be on daily treatment with INCS prior to screening and will continue their daily INCS with a stable dose as background treatment during the screening and throughout the study. Participants receiving rescue medication with SCS or/and surgery during this period will not be randomized. Randomization Visit is defined as Day 1. All subsequent visits will be calculated using this as a reference. Window for subsequent visits is +/-3 days. Assessments/procedures at a site visit are performed in the following order if applicable: PROs and other questionnaires; procedures; safety and laboratory assessments; IMP administration.
- b Participants who prematurely discontinue from the study prior to completing the planned treatment period (ie, ETD), will attend the ETD visit and follow the assessments for EOT as shown in this table, and will be requested to attend the remaining follow up visits per the protocol schedule with a +/- 5-day window until the EOS.
- c Follow-up period is not applicable for those participants entering a LTS18420 if a LTS18420 for itepekimab is initiated and approved by Health Authorities and country and/or local IRB/IEC. In the absence of a LTS18420 all participants enter the follow-up period.

- d* Home visits/phone calls will be conducted at the following timepoints: Week 6 (Visit 5), Week 8 (Visit 6), Week 10 (Visit 7), Week 14 (Visit 9), Week 16 (Visit 10), Week 18 (Visit 11), Week 20 (Visit 12), Week 22 (Visit 13), Week 26 (Visit 15), Week 28 (Visit 16), Week 30 (Visit 17), Week 32 (Visit 18), Week 34 (Visit 19), Week 38 (Visit 21), Week 40 (Visit 22), Week 42 (Visit 23), Week 44 (Visit 24), Week 46 (Visit 25), Week 48 (Visit 26), Week 50 (Visit 27).
- e* Window of +/-3 days applies to all visits during IMP administration. Follow up/EOS has a +/-7 day window.
- f* Separate consent to be obtained for optional procedures (whole blood DNA, and serum/plasma sampling for archival; nasal brushing for RNA and cytology, blood for genomic variant analyses), and potentially for HIV test, if specific consent is locally required.
- g* Past medical history including allergic comorbidities (asthma, aspirin sensitivity, allergic rhinitis etc), surgeries will be assessed including type and dates of sinonasal surgeries in the past. SCS use (number of courses, doses, way of administration and duration) in the past 2 years before Visit 1 and/or contraindication/intolerance to SCS, as well as long-term antibiotics use (>2 weeks) in the previous year will be entered in the eCRF.
- h* See Appendix 14 [Section 10.14](#) for AERD screening questionnaire.
- i* Details on actual or planned date, type, and outcome (whenever possible) of surgery will be recorded in a specific eCRF page. If surgery is performed during the study intervention period or follow-up, an AE or SAE page will be completed. Participants will be discontinued from study intervention and assessed as soon as possible using the procedures normally planned for the EOT visit. If surgery is scheduled after the planned EOS, a follow-up contact(s) may be required to document the surgery date and outcome.
- j* Nasal endoscopy (including use of decongestants before the procedure) will be performed after all other efficacy assessments have been completed for each visit and prior to IMP administration. Standard video sequences will be downloaded by the investigator to the central reader's secured Internet site. For eligibility central reading of Visit 1 will be used. At Visit 2 investigator reviews Visit 1 results from central reader to confirm inclusion criteria. Investigator then reconfirms eligibility based on review of Inclusion/Exclusion Criteria and by investigator's Visit 2 endoscopy local reading. This local read is solely for the purpose of confirming eligibility. The Visit 2 endoscopy will then be centrally read for NPS determination for outcome assessment.
- k* IMP (itepekimab or placebo) to be administered Q2W at the site. Participants should be monitored by site personnel for at least 30 minutes after administration of the first 3 IMP injections. Monitoring period may be extended as per country-specific requirements. Starting after Visit 4 (Week 4), IMP will be administered by the participant, caregiver, or healthcare professional at the participant's home or in a healthcare facility, depending on what is chosen, according to treatment allocation. If the participant or Investigator decides not to administer IMP at home, the IMP injections can be performed at the site. The last dose will be given 2 weeks prior to the planned EOT visit (Week 50).
- l* A CT scan should be performed at the Randomization Visit (up to 7 days before first administration of IMP), at Visit 14 (Week 24) +/- 7 days, and central reading will be used for comparison of baseline to Week 24. In countries for which a specific approval procedure for the CT scan is required by a different committee than the IEC/IRB, these countries will be exempted from all the planned study CT scans until approval from these committees is received. It is recommended to avoid the use of SCS as rescue therapy during Week 20 to Week 24. If a participant must use SCS during this period to control CRSwNP worsening/acute sinusitis based on Investigator judgment, the site should make every effort to schedule the Week 24 CT scan prior to SCS rescue therapy.
- m* An eDiary (ie, CRSwNP sinonasal symptom diary) is used for daily recording of nasal symptoms (from Visit 1 to EOS): 1) nasal congestion/obstruction, 2) anterior rhinorrhea (runny nose), 3) posterior rhinorrhea (post-nasal drip), 4) loss of sense of smell, 5) facial pain/pressure, and 6) headache. This device is dispensed at Visit 1, and information is downloaded from this device on the other indicated days. For endpoints defined using the data collected on the eDiary (such as NCS and TSS), baseline is defined as the average of the scores in the 7 days prior to randomization. Completion of a minimum of 4 out of 7 days is required prior to randomization.
- n* Spirometry will be performed according to ERS/ATS guidance only in participants with asthma. Pre-BD spirometry will be performed during a washout period of BDs according to their duration of action following the guidance of the ERS/ATS 2019 guideline. For example, withholding the last dose of salbutamol/albuterol or levosalbutamol/levalbuterol for at least 6 hours, withholding the last dose of ipratropium for at least 12 hours, withholding the last dose of LABA for at least 24 hours, and finally the last dose of ultra long-acting LABA (eg, vilanterol) or the last dose of LAMA should be withheld for at least 36 hours before spirometry is performed. The timing of washout will be verified before performing the measurements.
- o* During the study participants' responses to the SNOT-22; PGIS, PGIC, EQ-5D-5L, WPAI:SHp, PROMIS SD-SF-8b; ACQ-5 (in participants with asthma), and Leicester cough questionnaire will be recorded in an electronic format.
- p* Including blood pressure (mmHg), heart rate (beats per minute), respiratory rate (breaths per minute), body temperature (degrees Celsius). Height (cm) will be measured only at Screening. Weight (kg) will be measured at screening and Week 52/EOT.
- q* ECG will be collected and read locally.
- r* Hematology will include hemoglobin, hematocrit, platelet count, total red blood cell count, and total white blood cell count with differential. Serum clinical chemistry will include creatinine, blood urea nitrogen, glucose (fasting), lactate dehydrogenase, total cholesterol, total protein, calcium, albumin, total and direct bilirubin, ALT, AST, GGT, alkaline phosphatase, electrolytes (sodium, potassium, bicarbonate), CRP, and creatine phosphokinase. Blood eosinophils and CRP will be blinded after Visit 2.
- s* Specific gravity pH, glucose, protein, blood, ketones, nitrite, leukocyte esterase Microscopic examination (if blood or protein is abnormal).

